2.4 Treatments (study treatment, concomitant therapies, compliance)

The study drug and the study treatment is LDK378, as in the previous sections, reporting was based on FAS. The Safety Set will be used for all medication data summaries and listings unless otherwise specified.

2.4.1 Study treatment / compliance

Dose exposure and intensity

The Safety set will be used for summaries and listings of dose exposure and intensity unless otherwise specified.

Definitions of duration of exposure, cumulative dose, average daily dose, actual dose intensity (DI), planned dose intensity (PDI), relative dose intensity (RDI), percentage of days dosed, percentage of days the planned/intended dose was received, as well as intermediate calculations, include:

- Duration of exposure (days): last date of study drug – first date of study drug + 1 (periods of interruption are not excluded)
- Cumulative dose (mg): total dose of study drug taken by a patient in the study
- Number of dosing days (days): duration of exposure – number of zero dose days
- % Days dosed: $100 \times \text{number of dosing days} / \text{duration of exposure (days)}$
- % Days with planned dose: $100 \times \text{number of days with planned dose} / \text{duration of exposure (days)}$
- Average daily dose (mg/day): $\text{cumulative dose (mg)} / \text{number of dosing days (days)}$
- DI (mg/day): $\text{cumulative dose (mg)} / \text{duration of exposure (days)}$
- PDI (mg/day): $\text{cumulative planned dose (mg)} / \text{duration of exposure (day)}$
- RDI (%): $100 \times \text{DI (mg/day)} / \text{PDI (mg/day)}$

Duration of exposure to study drug, cumulative dose, and percentage of actual days dosed, percentage of days the planned/intended average daily dose was received, DI and RDI will be summarized. In addition, the duration of exposure to study drug will be categorized into time intervals); frequency counts and percentages of patients with exposure in each time interval will be presented. Frequency counts and percentages of patients who have dose reductions or interruptions, and the corresponding reasons, will be provided. The number of dose interruptions per patient, and the duration of dose interruptions (days) will be summarized. Cumulative dose, dose intensity and relative dose intensity of LDK378 will be listed by patient. Categories for relative dose intensity of LDK378 will be specified as < 0.5 , $\geq 0.5 - < 0.75$, \geq

0.75 - < 0.9, ≥ 0.9 - < 1.1 and ≥ 1.1 . The number and proportion of patients within each category will be presented.

Listings of all doses of the study drug along with dose change/interruption reasons will be produced.

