#### 6.1.1 Dosing regimen

LDK378 dose will be scaled by BSA. The dose will be adjusted to the nearest 50 mg, and the minimum dose will be 50 mg. LDK378 will be administered once daily by mouth, or by NG tube or G tube. For patients who are not able to swallow the capsules, or who will receive LDK378 through a NG tube or G tube, the capsules will be opened, and the contents mixed with an appropriate food or liquid. Further detailed instructions regarding capsule opening and administration will be provided to all study sites separate from this protocol.

The study site staff will inform each patient of their actual daily dose, and this will be recorded on the appropriate eCRF. The actual dose for each patient will be calculated using a body surface area (BSA) conversion as follows:

- Actual dose in mg = (planned dose level (mg/m^2) x BSA) rounded to the nearest 50 mg

Individual patient BSA will be calculated using their height and weight as per standard site procedure. The actual dose for Cycle 1 will be based on the BSA calculation at screening. Dosage adjustments for changes in BSA in subsequent cycles will be made as per standard site practice (e.g., if the BSA changes by  $\pm$  10% from the previous dose calculation).

[figure not shown]
Individual doses will consist of the minimum number of capsules possible given based on the available capsule sizes, and will be rounded to the nearest 50 mg.

The investigator should instruct the patient to take the LDK378 exactly as prescribed below. All dosages prescribed and dispensed to the patient, and all dose changes during the study must be recorded on the appropriate eCRF. Patients/guardians will be asked to complete a paper dosing diary starting Cycle 1 Day 1 and will return the paper dosing diary to the study site at the beginning of each subsequent cycle (cycle 2 and on). A new diary will be dispensed to the patient at the beginning of each new cycle.

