## 10.3 Treatments (study treatment, concomitant therapies, compliance)

### 10.3.1 Study treatment

The actual dose and duration in days of LDK378 treatment, as well as the dose intensity (computed as the ratio of actual dose received and actual duration) and the relative dose intensity (computed as the ratio of dose intensity and planned dose received/planned duration), will be listed and summarized by means of descriptive statistics in the clinical study report. The summary data will be presented for each treatment cycle individually, as well as for all study days as a single category. The FAS will be used.

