#### 10.7.1.5 Supportive analyses for secondary objectives

##### 10.7.1.6 Tolerability

Tolerability of LDK378 will be assessed by summarizing the number of dose interruptions and dose reductions. Reasons for dose interruption and dose reductions will be listed by patient and summarized. Cumulative dose, dose intensity and relative dose intensity of LDK378 will be listed by patient and summarized. Categories for relative dose intensity of LDK378 will be specified as  $< 0.5$ ,  $\geq 0.5 - < 0.75$ ,  $\geq 0.75 - < 0.9$ ,  $\geq 0.9 - < 1.1$  and  $\geq 1.1$ . The number and proportion of patients within each category will be presented.

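### SAP 2.4.1 computes relative dose intensity in percent but classes it with fractional cut-offs, and summarizes cumulative dose and dose intensity in mg for groups defined by mg/m²

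*SAP*

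**What the plan says.** **RDI scale.** SAP 2.4.1 defines RDI in percent, as 100 × DI/PDI, where PDI is planned dose intensity. Further down the same section, "Categories for relative dose intensity of LDK378 will be specified as" introduces five classes: below 0.5, 0.5 to below 0.75, and then "0.75 - < 0.9, ≥ 0.9 - < 1.1 and ≥ 1.1". Protocol 10.3.1 has no factor of 100: it describes "the relative dose intensity (computed as the ratio of dose intensity and planned dose received/planned duration". Protocol 10.7.1.6 gives the same five fractional classes. SAP Table 4-1, which lists departures from the protocol's analyses, has two entries, both about best overall response.

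**Dose units.** Protocol 6.1.1 states "LDK378 dose will be scaled by BSA", with rounding to the nearest 50 mg. SAP 2.1 and 2.1.1 present summaries by treatment group, which is a mg/m² level plus regimen. SAP 2.4.1 nevertheless works in absolute amounts: "Cumulative dose (mg): total dose of study drug taken by a patient in the study", with DI as that total divided by days of exposure. Cumulative dose, DI and RDI are among the items it summarizes. Average daily dose and PDI are defined there but are not in that list.

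**Role.** Under tolerability, Protocol 10.7.1.6 says "Cumulative dose, dose intensity and relative dose intensity of LDK378 will be listed by patient and summarized".

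**The concern.** The class rule and the variable it classes are on different scales within one SAP section. The protocol is consistent with itself, so the mismatch arose when the SAP added the factor of 100. SAP Section 2 is also the text to be carried into the study report, so the error can travel with it.

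The second issue is one of meaning. Patients range from 12 months to under 18 years, with an eligibility floor of 0.35 m² BSA. Two fully compliant children at the same dose level can have very different mg/day values, and a group mean in mg/day depends on which ages were recruited to that level. A reader of the report could take a difference in mean DI between dose levels or regimens for a difference in dose delivered per m² when part of it is body size.

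**Working it through.** The plan states no figure to reproduce here. The check applies the SAP's own formulas.

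**1. RDI classes read literally**

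| Actual/planned | Class as a ratio | SAP RDI (%) | Class with the SAP cut-offs |
|---|---|---|---|
| 0.30 | <0.5 | 30 | ≥1.1 |
| 0.60 | 0.5–<0.75 | 60 | ≥1.1 |
| 0.80 | 0.75–<0.9 | 80 | ≥1.1 |
| 1.00 | 0.9–<1.1 | 100 | ≥1.1 |
| 1.20 | ≥1.1 | 120 | ≥1.1 |

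To stay out of the top class a patient needs an RDI below 1.1%. That is less than one full planned dose per 1/0.011 ≈ 91 days. On the ratio scale the same five patients fill five distinct classes.

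**2. DI in mg/day at one dose level**

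Inputs: 500 mg/m² fed (SAP Table 2-1); dose = level × BSA, rounded to 50 mg (Protocol 6.1.1); full compliance. The upper BSA of 1.7 m² is an assumption: it is the protocol's average adult figure (6.2.1), used for an adult-sized adolescent.

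- BSA 0.4 m²: 500 × 0.4 = 200 mg/day
- BSA 1.0 m²: 500 × 1.0 = 500 mg/day
- BSA 1.7 m²: 500 × 1.7 = 850 mg/day

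Spread at identical mg/m² and compliance: 850/200 = 4.25-fold. If the largest patient were only 1.0 m², it would be 500/200 = 2.5-fold. The gap that the table should display, between the lowest and highest fed levels, is 500/320 = 1.56-fold.

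**3. Consequence for ordering**

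- Across levels: a 1.7 m² patient at 320 mg/m² takes 544, rounded to 550 mg/day. A 0.8 m² patient at 500 mg/m² takes 400 mg/day. The lower dose level shows the higher DI.
- Group means: with equal compliance and ignoring rounding, the 320 and 500 mg/m² groups change order if their mean BSAs differ by a factor above 1.56 (for example 320 × 1.7 = 544 against 500 × 1.0 = 500).
- Within a level: at 500 mg/m², a 0.6 m² patient taking everything has a DI of 300 mg/day. A 1.7 m² patient taking 60% has 0.6 × 850 = 510 mg/day. In mg/m²/day the two read 300/0.6 = 500 and 510/1.7 = 300, which is the right order.

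**4. What is not affected**

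Percentage of days dosed contains no mg. In RDI, body size cancels between DI and PDI provided that planned and actual dose use the same BSA. SAP 2.4.1 does not say which BSA defines planned dose.

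**The case against.** SAP 2.1 says that the data will be analyzed according to Section 10 of the protocol, where RDI is a plain ratio. With no change recorded in Table 4-1, a careful programmer would read 0.5 as 50%. A table with every patient in one cell would also be noticed. This stands: a reader might infer that all patients will be reported in the top class, but that follows only from literal programming that nobody checks. The specification still contradicts itself and should not rely on silent correction.

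On units, mean mg/day is a correct record of drug taken and still carries dose. RDI and percentage of days dosed already describe delivery against plan, by-patient listings are provided, and SAP 2.4.1 specifies no comparison of DI between groups. This also stands. A reader might infer that the group means show body size and not dose. The documents support only that they mix dose level, compliance and body size. The SAP does, however, divide dose by BSA in the safety-set rule (2.2) and the dose-proportionality model (2.10), so leaving it out here is inconsistent with its own practice.

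A reader might also infer that growth will push children into the over-dosing class. That would require planned dose to be fixed at baseline BSA, which no section says; Protocol 6.1.1 provides for dose adjustment as BSA changes. Even then, RDI in SAP 2.4.1 is cumulative: a 10% dose rise at the midpoint of exposure gives 0.5 × 100 + 0.5 × 110 = 105%, not 110%.

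**Conclusion.** Two points hold. First, SAP 2.4.1 has a percent/fraction mismatch: applied as written, it puts every RDI of 1.1% or more in the top class and empties the table of information. The intended scale can be recovered from Protocol 10.3.1 and 10.7.1.6, so this is a correctable slip and not an unavoidable result. Second, the group summaries of cumulative dose and DI are confounded by body size. At 500 mg/m² and full compliance the spread is 4.25-fold between 0.4 and 1.7 m² (2.5-fold if the upper BSA is 1.0 m²), against 1.56-fold between the lowest and highest fed levels.

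The sizes are illustrative: the documents give the 0.35 m² floor and the age range but no observed BSA distribution, and how far real group means are distorted depends on the age mix at each level. The effect is confined to descriptive exposure and tolerability tables. The Bayesian logistic regression for dose-limiting toxicity and the response-rate analyses do not use these quantities.

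**What to change.** In SAP 2.4.1:

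1. State the RDI classes as <50, 50–<75, 75–<90, 90–<110 and ≥110%, or drop the factor of 100 and keep the protocol's cut-offs.
2. Add cumulative dose in mg/m² (the sum of each daily dose divided by BSA) and DI in mg/m²/day (that sum divided by duration of exposure). Use the last BSA on or before each dosing date, which is the rule already in SAP 2.2. The mg versions can stay alongside.
3. State that planned dose is computed from that same BSA, so that body size cancels in RDI.

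The cost is a few lines of SAP text and a small amount of extra programming. No new data are needed: Protocol 7.2.2.3 and Table 7-1 already collect BSA at screening, on Day 1 of Cycles 2 to 16, and at on-site visits after that. Protocol 10.3.1 and 10.7.1.6 fix no mg unit, so no protocol change is needed.

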2.4.2 Concomitant and post therapies

The Safety set will be used for the summaries and listings of concomitant and post therapies unless otherwise specified.

Concomitant therapy

Concomitant therapies are defined as any medications (excluding study drug, prior antineoplastic treatments) and significant non-drug therapies (including physical therapy and blood transfusions) administered in the study and recorded in the Concomitant Medications/significant non-drug therapies eCRF.

These therapies will be coded using the WHO Drug Reference Listing (WHO DRL) dictionary that employs the WHO Anatomical Therapeutic Chemical (WHO ATC) classification system. All summaries will be tabulated using frequency counts and percentages.

Concomitant therapies will be summarized by ATC class and preferred term. These summaries will include 1) medications and non-drug therapies starting on or after the start of study drug but starting no later than 30 days after last dose of study drug and 2) medications and non-drug therapies starting prior to the start of study drug but continuing after the start of study drug.

All therapies will be listed. Any therapies starting and ending prior to the start of study drug or starting more than 30 days after the last date of study drug will be flagged in the listing.

Frequency and percentage of patients using medications known to prolong the QT interval concomitantly with study drug will be summarized by ATC class and preferred term.

Antineoplastic therapy after discontinuation of study drug

All summaries will be tabulated using frequency counts and percentages using the FAS.

Antineoplastic therapies, including medications, surgeries, and radiotherapies, initiated after discontinuation of study drug will be summarized and listed by Anatomical Therapeutic Chemical (ATC) class and preferred term.

2.5 Analysis of the primary objective

The primary objective of the study is to estimate the MTD/RDE separately on a daily dose of LDK378 when administered orally as a single agent to pediatric patients with an advanced malignancy carrying genetic alteration of ALK. The corresponding primary analysis method is an adaptive Bayesian logistic regression model (BLRM) guided by the escalation with overdose control (EWOC) principle (Neuenschwander et al 2008). The MTD/RDE is determined to be 510 mg/m² for fasted regimen and 500 mg/m² for fed regimen.

2.5.1 Primary endpoint

Variable

The primary endpoint is the incidence of dose limiting toxicities (DLTs) in Cycle 1. The MTD is defined as the maximum dose for a given schedule that is expected to cause DLTs in no more than 33% of patients during the first cycle of treatment. Estimation of the MTD during the dose-escalation phase of the study will be based upon the estimation of the probability distribution of the incidence of DLT in cycle 1 in patients in the dose-determining set.

2.5.2 Statistical hypothesis, model, and method of analysis

An adaptive BLRM with two parameters guided by the EWOC principle will be used to make dose recommendations and estimate the MTD separately during the fasted dose escalation and the fed dose escalation of the study.

Statistical model for the fasted dose escalation

The dose-toxicity (DLT) relationship in the fasted dose-escalation phase of the study will be described by the following Bayesian logistic regression model:

$$\text{logit}(\pi_{(d)}) = \log(\alpha) + \beta \log(d/d^*), \quad \alpha > 0, \beta > 0 \quad [1]$$

where $\text{logit}(\pi_{(d)}) = \ln(\pi_{(d)}/(1-\pi_{(d)}))$, $\pi_{(d)}$ is the probability of a DLT at dose d . Doses are rescaled as d/d^* with reference dose $d^* = 400 \text{ mg/m}^2$ of LDK378. Consequently α is equal to the odds of toxicity at d^* . Note that for a dose equal to zero, the probability of toxicity is zero. The Bayesian approach requires the specification of prior distributions for the model parameters.

See Section 14.1.2 of the protocol for the prior specification for the fasted dose escalation.

Statistical model for the fed dose escalation

The same 2-parameter form of the BLRM described in equation [1] will be used to estimate the dose-DLT relationships separately for fasted and fed patients. Dose escalation in fed patients will begin once the MTD/RDE is determined in fasted patients. Data from fasted patients will be utilized to formulate a prior distribution for the BLRM parameters for fed patients.

Methodology for updating down-weighting:

Since fed patients will be enrolled after all the patients in dose escalation fasted part will have potentially completed cycle 1 (or have experienced DLT), and since it can be assumed that there is a certain grade of similarity in dose toxicity relationship between these two regimen, the updating of the prior distribution of the BLRM parameters for fed patients will be evidence based. In particular, at the time of starting the fed-patients cohort, DLT data from fasting patients will be included into the BLRM and discounted (assuming substantial between regimen heterogeneity) to account for potential differences between fed and non-fed patients, while assuming some degree of similarity.

Specifically, the DLT information from fasted patients will be incorporated through down-weighting the data directly. The weight “ w ” (see [Neuenschwander et al 2010](#)) that will be assigned to each fasted patient included in the DDS is given in the following formula:

$$w = \frac{1}{1 + 2n\tau^2/\sigma^2} = \frac{1}{1 + 2n/n_\infty^*}$$

where n is the sample size of historical data (i.e. the number of fasted patients in the DDS), σ is the “outcome standard deviation” for one observation and τ is the assumed between regimen standard deviation. n_∞^* can be interpreted as the maximum prior effective sample size under infinite historical information. σ was chosen as 2 and τ was set as 2, to correspond to a substantial heterogeneity due to the different dosing regimens.

When all patients in the fasted dose escalation have completed at least one cycle, the weights will be calculated based on the data available at that time point.

Dose recommendation

After each cohort is completed, the posterior distributions for the probabilities of DLT at different dose levels are obtained. The results of this analysis are summarized in terms of the estimated probabilities that the true rate of DLT at each dose-level will lie within each of the following intervals:

- (0, 0.16) under-dosing.
- (0.16, 0.33) targeted toxicity.
- (0.33, 1.00) excessive toxicity.

Following the principle of EWOC, after each cohort of patients the recommended dose is the one with the highest posterior probability of the DLT rate falling in the target interval (16%, 33%) among the doses fulfilling EWOC, i.e. it is unlikely (< 25% posterior probability) that the DLT rate at the dose falls in the excessive toxicity interval. In addition, the maximum dose escalation for the fasted regimen is limited to 50% before reaching 450 mg/m², and to 25% after reaching 450 mg/m², which correspond to the adult MTD. Dose escalations for the fed dose escalation part will be limited to a 25% or smaller increase above the prior fed dose level.

Note that the dose that maximizes the posterior probability of targeted toxicity is the best estimate of the MTD, but it may not be an admissible dose according to the overdose criterion if the amount of data is insufficient. If vague prior information is used for the probabilities of DLT, in the early stages of the study this escalation procedure will reflect a cautious strategy. The dose recommended by the adaptive Bayesian logistic model may be regarded as guidance and information to be integrated with a clinical assessment of the toxicity profiles observed at the time of the analysis in determining the next dose level to be investigated.

Details of the criteria for dose escalation and the determination of the MTD are provided in Section 6.2.3 of the study protocol.

Dose Expansion

Upon completion of the first cycle of treatment for at least 10 patients within the dose expansion part, if the observed DLT rate exceeds 33%, the BLRM will be re-run to confirm that the estimated MTD/RDE on either regimen still satisfies the overdose criteria of the model. If the dose fails to satisfy the criteria a change to the dose under study may be made according to the Bayesian model recommendation, and review of the clinical data. DLTs will be listed and their

incidence summarized by primary system organ class, worst grade based on the CTCAE version 4.03, type of adverse event, and by treatment. The DDS will be used for these summaries.

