### **IRB/IEC/REB Approval**

A copy of this amended protocol will be sent to the Institutional Review Board (IRBs)/Independent Ethics Committee (IECs) and Health Authorities.

The changes described in this amended protocol require IRB/IEC approval prior to implementation.

The changes herein affect the Informed Consent. Sites are required to update and submit for approval a revised Informed Consent that takes into account the changes described in this protocol amendment.

## Amendment 6

The dose escalation phase of this study has been completed and 40 patients have been enrolled and treated (25 fasted and 15 fed). Similar recommended LDK378 doses (RDE) were established for both fasted state (510 mg/m^2 once daily, declared on 4 Dec 2014), and fed state (500 mg/m^2 once daily, declared on 12 April 2016). As fed state is more convenient for pediatric patients, it has been decided to complete the recruitment of the expansion phase using this preferred regimen only. The expansion phase, to confirm the dose, is currently recruiting and as of 22 September 16, 20 patients have been enrolled (7 fasted and 13 fed). Overall, 19 patients are currently ongoing in total (6 recruited in escalation phase and 13 in the expansion phase).

The primary purpose of this amendment is to revise the dose reduction steps for LDK378. Considering the recommended doses established for fed and fasted state are similar, the dose reduction schedule has been revised to be applicable for both states.

In addition, the schedule of assessments has been revised to reduce frequency of on-site visits after cycle 16: on-site visits on day 1 of odd numbered cycles are replaced by phone calls and local laboratory tests for safety assessments.

Moreover, the pre-dose PK sample and the post-dose ECGs collection at Cycle 1 Day 1 have been removed in the expansion phase as they were no longer required at this time point as no correlation is planned in the expansion.

At last, editorial changes and text corrections were made for clarification, where required.

Changes to specific sections of the protocol are shown in the track changes version of the protocol using red strike through font for deletions and red underlined font for insertions.

The following sections were updated:

- Section 6.3.1: Table 6-3 dose reduction steps for LDK378 was revised based on the recommended dose for expansion

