### Dose recommendation

After each cohort is completed the posterior distributions for the probabilities of DLT at different dose levels are obtained. The results of this analysis are summarized in terms of the estimated probabilities that the true rate of DLT at each dose-level will lie within each of the following intervals:

- (0, 0.16) under-dosing.
- (0.16, 0.33) targeted toxicity.
- (0.33, 1.00) excessive toxicity.

Following the principle of EWOC, after each cohort of patients the recommended dose is the one with the highest posterior probability of the DLT rate falling in the target interval (16%, 33%) among the doses fulfilling EWOC, i.e. it is unlikely ( $< 25\%$  posterior probability) that the DLT rate at the dose falls in the excessive toxicity interval. In addition, the maximum dose escalation for the fasted regimen is limited to 50% before reaching  $450 \text{ mg/m}^2$ , and to 25% after reaching  $450 \text{ mg/m}^2$ , which correspond to the adult MTD. Dose escalations for the fed dose escalation part will be limited to a 25% or smaller increase above the prior fed dose level.

Note that the dose that maximizes the posterior probability of targeted toxicity is the best estimate of the MTD, but it may not be an admissible dose according to the overdose criterion if the amount of data is insufficient. If vague prior information is used for the probabilities of DLT, in the early stages of the study this escalation procedure will reflect a cautious strategy.

The dose recommended by the adaptive Bayesian logistic model may be regarded as guidance and information to be integrated with a clinical assessment of the toxicity profiles observed at the time of the analysis in determining the next dose level to be investigated.

Details of the criteria for dose escalation and the determination of the MTD are provided in [Section 6.2.3](#).

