### **Dose expansion**

Upon completion of the first cycle of treatment for at least 10 patients within the dose expansion part, if the observed DLT rate exceeds 33%, the BLRM will be re-run to confirm that the estimated MTD/RDE on either regimen still satisfies the overdose criteria of the model. If the dose fails to satisfy the criteria a change to the dose under study may be made according to the Bayesian model recommendation, after review of the clinical data.

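### The expansion check re-runs the dose-toxicity model only when the observed DLT rate exceeds 33%, with no regimen named, so a dose that fails the plan's own 25% overdose criterion can go unchecked

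*SAP*

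**What the plan says.** Protocol 10.4.2 (Dose expansion) sets the time of the check: "Upon completion of the first cycle of treatment for at least 10 patients within the dose expansion part". It then sets the condition: "if the observed DLT rate exceeds 33%, the BLRM will be re-run". SAP 2.5.2 repeats both; its condition reads "if the observed DLT rate exceeds 33%, the BLRM will be re-run to confirm that the estimated MTD/RDE on either regimen" still meets the overdose criteria. If the model then fails its overdose criteria, the dose may be changed after clinical review. Neither document says whether the observed rate is computed by regimen or over all expansion patients, or whether the check is made once or repeatedly after the tenth patient.

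The overdose criterion is in the same sections, under Dose recommendation. A dose is admissible if "it is unlikely (< 25% posterior probability) that the DLT rate at the dose falls in the excessive toxicity interval"; that interval is "0.33, 1.00) excessive toxicity". SAP 2.5.2 uses the BLRM to "estimate the dose-DLT relationships separately for fasted and fed patients".

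The expansion part did hold both regimens. Amendment 5 records 5 expansion patients, all fasted, on 17 February 2016. Amendment 6 dates the fed RDE to 12 April 2016 and reports that by 22 September 2016 "20 patients have been enrolled (7 fasted and 13 fed").

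**The concern.** The rule that decides whether to look is of a different kind from the rule that decides whether the dose is acceptable. With little prior information, an observed rate near 33% leaves roughly an even chance that the true rate is above 33%, about twice the 25% limit. The model can therefore be left unrun in data where it would have returned a failure.

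The regimen matters because the two curves are fitted separately. SAP 2.5.2 sets both σ and τ at 2, so each fasted patient enters the fed prior with weight 1/(1 + 2n). All n fasted patients together contribute n/(1 + 2n), which is less than half a patient. The fed model depends almost wholly on fed data, yet the patient count that starts the check names no regimen.

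What is at stake is the primary objective, the MTD/RDE in each feeding state. SAP 2.5.1 estimates the MTD from the dose-determining set, whose definition in SAP 2.2 refers to the escalation phase. SAP 2.1 names the dose-DLT analysis as an exception to pooling escalation with expansion data. The gate is the only stated route by which expansion DLTs reach the model. If it stays shut, the final statement on 510 mg/m² fasted and 500 mg/m² fed need not use the expansion patients treated at those doses.

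**Working it through.** The documents give no operating characteristic for this check, so there is no figure to reproduce.

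**Inputs from the documents.** Gate: observed rate above 33%. Earliest look: 10 expansion patients. Criterion: P(DLT rate > 0.33) below 0.25. Minimum at a dose before it can become the MTD/RDE: 6 patients (protocol 6.2.3). Regimen counts: Amendments 5 and 6.

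**Assumptions.** The BLRM prior is redacted and escalation DLT counts are not given. I use three weak Beta(a, b) priors as surrogates and a range of assumed escalation results. The expansion size of 25 is illustrative.

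**Step 1: gate against criterion.** For x DLTs in n patients, P(rate > 0.33) = 1 − F(0.33; a + x, b + n − x), where F is the Beta distribution function. The gate stays shut in every row (3/10 = 30%, 8/25 = 32%).

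| Data at the dose | Total | Beta(0.25, 0.75) | Beta(0.5, 0.5) | Beta(1, 1) |
|---|---|---|---|---|
| 3/10, no escalation data | 3/10 | 0.370 | 0.436 | 0.482 |
| 0/6 escalation + 3/10 | 3/16 | 0.084 | 0.109 | 0.137 |
| 1/6 escalation + 3/10 | 4/16 | 0.212 | 0.254 | 0.291 |
| 1/6 escalation + 8/25 | 9/31 | 0.292 | 0.326 | 0.352 |

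**Step 2: could the dose have been selected in the first place?** Escalation data alone give:

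| Escalation data | Beta(0.25, 0.75) | Beta(0.5, 0.5) | Beta(1, 1) |
|---|---|---|---|
| 0/6 | 0.009 | 0.025 | 0.061 |
| 1/6 | 0.141 | 0.204 | 0.270 |
| 2/6 | 0.442 | 0.528 | 0.578 |

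A 2/6 start already fails under all three priors, and 1/6 fails under the uniform prior, so those states should not be used as examples of a selected dose. The 1/6 start is admissible under the first two priors. With 8/25 added, those give 0.29 and 0.33, above 0.25, and the gate is shut. The 3/10 row without escalation data shows the mismatch but leaves out the 6 or more patients required at the dose.

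**Step 3: a two-parameter model as a cross-check.** A BLRM with reference dose 400, evaluated at 500, was run under assumed priors: log α centred at logit 0.10, 0.25 or 0.33 with SD 2, and log β with mean 0 and SD 1. With no escalation data, 3/10 gives 0.33 to 0.42. With assumed escalation results of 0/3, 0/4, 1/6 it gives 0.07 to 0.09; with 0/3, 1/4, 2/8 it gives 0.20 to 0.24. The last two pass. The 8/25 example was worked only in the Beta surrogate.

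**Step 4: how often the gate stays shut, one regimen.** At n = 10 it opens at 4 DLTs, so it stays shut with probability P(X ≤ 3): 0.57, 0.38 and 0.17 at true rates of 0.33, 0.40 and 0.50. At n = 20 it opens at 7; at a true rate of 0.40 it stays shut 25% of the time.

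With a vague prior, n = 10 and no escalation data, the criterion fails from 3 DLTs. The share of failures missed is P(X = 3)/P(X ≥ 3):
- true rate 0.33: 0.261/0.693 = 38%
- true rate 0.40: 0.215/0.833 = 26%
- true rate 0.50: 0.117/0.945 = 12%

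**Step 5: if the rate is taken over both regimens.** The first 10 expansion patients held 5 to 7 fasted: 5 were enrolled before any fed patient, and there were 7 in all by September 2016. The probability of a shut gate is that of the two binomial counts summing to 3 or fewer (n = 10) or 6 or fewer (n = 20).

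| Fasted | Fed | Gate shut |
|---|---|---|
| 7 at 15% | 3 at 50% | 78% |
| 7 at 20% | 3 at 50% | 68% |
| 5 at 20% | 5 at 50% | 51% |
| 7 at 20% | 13 at 50% | 25% |
| 7 at 40% | 13 at 20% | 72% |

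The regimen with fewer patients is the one most easily hidden. A result of 3/3 fed with 0/7 fasted (30% overall) would not open the gate.

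**The case against.** Four counter-arguments carry weight.

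First, a reader might infer that the rate is pooled over regimens. The text does not say so. It refers to either regimen, and the SAP defines a treatment group by dose and regimen and tabulates DLTs by treatment group. A by-regimen reading is at least as natural. What stands is that the rule is silent; the figures in step 5 apply only under the pooled reading.

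Second, a reader might infer that a failing dose would usually be missed. Step 4 does not support that: on one regimen at n = 10 with a vague prior, the miss rate is 26% at a true rate of 0.40 and 12% at 0.50. With reassuring escalation data, 3/10 passes and nothing is missed. Ten is also a minimum, and the gate works better at 20.

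Third, running the model regardless has a price. At a true rate of 0.25, with a vague prior and n = 10, the criterion fails 47% of the time, against 22% for the gate opening. This is a fair warning about acting on a single small look. It does not argue against reporting the probability at the end.

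Fourth, Amendment 8 states that recruitment was complete in October 2017, and the SAP records both RDEs as determined. Protocol 10.4 gives MTD/RDE estimation as the aim of the escalation part, and protocol 4.4 separately allows termination for excessive toxicity. So removing the gate now protects no patient. What remains is the quality of the final answer, where the extra information is cheap.

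**Conclusion.** The point holds as a mismatch between gate and criterion, and as an undefined regimen. The plan can leave its overdose criterion unevaluated in data where it would fail. Under the surrogate priors that would have admitted the dose at 1/6, the overdose probability with 8/25 added is 0.29 to 0.33 (0.35 if the uniform prior is included), against a limit of 0.25, with no re-run.

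The documents do not support saying that this happens in most cases, or that the rate is pooled by design. The frequency depends on the redacted BLRM prior and on escalation DLT counts that are not given. Across the assumed Beta prior-plus-escalation cases at n = 10, averaged over the prior, the share of failing doses missed runs from 0 to 39%. The numerical examples rest on Beta surrogates, so their size carries only moderate confidence. The mismatch itself is plain from the text.

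**What to change.** At the final analysis, re-run the BLRM separately for fasted and fed, adding cycle-1 DLT data from evaluable expansion patients at 510 mg/m² fasted and 500 mg/m² fed, whatever the observed rate. Evaluability can follow the same minimum-exposure and 21-day observation rules as the dose-determining set. For each regimen, report P(DLT rate > 33%) beside the 25% criterion and beside the escalation-only estimate. State that any observed expansion DLT rate is calculated by regimen. Record this in SAP 2.5.2 and as a row in the SAP Section 4 table of changes, leaving the escalation-phase definition of the dose-determining set as it is for the primary model.

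The cost is two runs of an existing program and one SAP paragraph. The downside is a published posterior that may look less favourable than the escalation-only figure. The change concerns analysis and reporting only; it proposes no dose and no clinical rule.
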